2 SIGNATURE PAGE

Study Title: A 12-Week, Phase 2, Randomized, Placebo-Controlled, Double-Blind Study to Assess the Efficacy, Safety, and Tolerability of Gemcabene in Subjects with Hypercholesterolemia Not Adequately Controlled on High-Intensity or Moderate-Intensity Stable Statin Therapy (ROYAL-1)

Study Number: GEM-301

Prepared by:	PI [Redacted] PI [Redacted]	PI [Redacted]
Reviewed by:	PI [Redacted] PI [Redacted]	PI [Redacted]
Approved by:	PI [Redacted] Gemphire Therapeutics Inc.	PI [Redacted]
Approved by:	PI [Redacted] Gemphire Therapeutics Inc.	PI [Redacted]

Document History – Major changes compared to previous versions of the analysis plan

Version	Date	Changes
Final 1.0	17-Apr-17	N/A
Amendment 1.0	10-Jul-17	
Added that potentially clinically significant laboratory values, single occurrences, will also be summarized by statin-intensity stratum.
 
Added information on imputing drug interruptions with partial start/stop dates to be 1 day in length along with technical comments regarding assignment.
 
Added that we are summarizing days on treatment and days drug was interrupted for.
 
Added 2 urinalysis parameters to PCS criteria.
 
Updated PPS section.
 
Edited text to reflect hsCRP and TG being analyzed using ranked ANCOVA.

3 LIST OF ABBREVIATIONS AND DEFINITIONS OF TERMS

ACE	angiotensin-converting enzyme
AE	adverse event
ALP	alkaline phosphatase
ALT	alanine aminotransferase
ANCOVA	analysis of covariance
Apo	apolipoprotein
AST	aspartate aminotransferase
ATC	anatomical therapeutic chemical
BMI	body mass index
BUN	blood urea nitrogen
CFBL	change from baseline
CI	confidence interval
CRF	case report form
CVD	cardiovascular disease
DBP	diastolic blood pressure
DPP	dipeptidyl peptidase
ECG	electrocardiogram
eCRF	electronic case report form
ET	early termination
FAS	Full Analysis Set
FPG	fasting plasma glucose
GFR	glomerular filtration rate
GGT	gamma-glutamyl transferase
HbA1c	hemoglobin A1c
HBV	hepatitis B virus
HCV	hepatitis C virus
HDL-C	high-density lipoprotein cholesterol
HIV	human immunodeficiency virus
HoFH	homozygous familial hypercholesterolemia

hsCRP	high-sensitivity C-reactive protein
LDH	lactate dehydrogenase
LDL-C	low-density lipoprotein cholesterol
LOCF	last observation carried forward
Lp(a)	Lipoprotein(a)
LSM	least-squares mean
MAO	monoamine oxidase
MedDRA	Medical Dictionary for Regulatory Activities
NCEP ATP-III	National Cholesterol Education Program Adult Treatment Panel III
NGAL	neutrophil gelatinase-associated lipocalin
OR	odds ratio
PCS	potentially clinically significant
PCSK9	proprotein convertase subtilisin/kexin type 9
PPS	Per-Protocol Set
PT	preferred term
QD	once daily
QTcB	QT interval corrected for heart rate with Bazett's formula
QTcF	QT interval corrected for heart rate with Fridericia's formula
SAA	serum amyloid A
SAE	serious adverse event
SAS	Safety Analysis Set
SBP	systolic blood pressure
SD	standard deviation
SE	standard error
SOC	system organ class
TC	total cholesterol
TEAE	treatment-emergent adverse event
TG	triglyceride
TSH	thyroid-stimulating hormone
ULN	upper limit of normal

VLDL-C very low-density lipoprotein cholesterol
WHO World Health Organization

4 INTRODUCTION

The purpose of this statistical analysis plan is to describe the framework for the reporting, summarization, and statistical analysis methodology of the safety and efficacy parameters measured throughout the study. It is based on Protocol GEM-301 (Amendment 3) dated 05 Oct 2016.

5 TRIAL OBJECTIVES

5.1 Primary Objectives

The primary objective of this study is to assess the low-density lipoprotein cholesterol (LDL-C) lowering of gemcabene 600 mg once daily (QD) compared to placebo in subjects with hypercholesterolemia not adequately controlled on high-intensity or moderate-intensity stable statin therapy treated for 12 weeks.

5.2 Secondary Objectives

The secondary objectives of this study are the following:

- to assess the LDL-C lowering of gemcabene 600 mg in (1) subjects on high-intensity stable statin therapy; and (2) subjects on moderate-intensity stable statin therapy treated for 12 weeks;
- to assess the safety and tolerability of gemcabene 600 mg in all subjects combined and separately in (1) subjects on high-intensity stable statin therapy; and (2) subjects on moderate-intensity stable statin therapy treated for 12 weeks; and
- to assess the effect of gemcabene on other lipid and apolipoprotein (Apo) parameters, high-sensitivity C-reactive protein (hsCRP), serum amyloid A (SAA), adiponectin, fibrinogen, and cardiovascular risk over 12 weeks of treatment.

5.3 Exploratory Objectives

The exploratory objectives of this study are the following:

- [REDACTED]
- [REDACTED]
- [REDACTED]

6 STUDY DESIGN CONSIDERATIONS

6.1 Study Design

This is a Phase 2, randomized, placebo-controlled, double-blind, multicenter study with a duration of up to 26 weeks with 12 weeks of study drug treatment. The study will consist of a Pre-Screening Visit (only for subjects requiring a wash-out period), a Screening Visit, a Treatment Period, and a Follow-up Visit.

Table 1. Overview of Study Periods

	Wash-out Period (for subjects requiring wash-out)	Screening Visit	Treatment Period
Study Days	Day -70 to -15, inclusive	Day -14 to -1, inclusive	Day 1 to 85, inclusive

Approximately 104 subjects will participate in the study at up to 20 sites in the United States. Subjects are required to be on either a high-intensity stable statin regimen (atorvastatin at 40 or 80 mg QD, or rosuvastatin at 20 or 40 mg QD) or a moderate-intensity stable statin regimen (atorvastatin at 10 or 20 mg QD, rosuvastatin at 5 or 10 mg QD, or simvastatin at 20 or 40 mg QD) with or without ezetimibe 10 mg QD for at least 12 weeks prior to the Screening Visit. Further, subjects must have a fasting LDL-C value ≥ 100 mg/dL (2.59 mmol/L) and a TG value < 500 mg/dL (5.65 mmol/L) at the Screening Visit, while on a stable, low-fat, low-cholesterol diet.

A wash-out period will be required for eligible subjects taking any lipid-regulating therapies or supplements except for atorvastatin at 10, 20, 40, or 80 mg QD, rosuvastatin at 5, 10, 20, or 40 mg QD, simvastatin at 20 or 40 mg QD, and/or ezetimibe at 10 mg QD. For subjects requiring a wash-out period, the Pre-Screening Visit will be their first study visit and will occur prior to the Screening Visit. The time between the Pre-Screening Visit and Screening Visit will depend on the required wash-out period duration which varies according to the status of a given subject's current lipid-regulating therapy. Specifically, PCSK9 inhibitors require an 8-week wash-out period, fibrates require a 6-week wash-out period, and niacins along with other lipid-regulating therapies including bile acid sequestrants require a 4-week wash-out period. For eligible subjects that do not require a wash-out period, the Screening Visit will be their first study visit.

Subjects will be randomized on Day 1 in a 1:1 ratio (gemcabene 600 mg to placebo). Randomization will be stratified by baseline statin-intensity regimen (moderate or high) and diabetes status (yes or no), both of which are recorded on the Medical History form at the subject's first visit (Pre-Screening or Screening Visit) and updated, when appropriate, at the Screening Visit. Subjects defined as diabetic are those receiving concomitant anti-diabetic medication at screening. Randomization within a baseline statin-intensity stratum will be capped at 52 subjects. By further stratifying on diabetes status at baseline, diabetic subjects will be evenly distributed across treatment groups within each statin-intensity stratum.

Post-randomization clinic visits will occur at Weeks 2, 4, 8 and 12. The Follow-up Visit will occur 4 weeks (± 3 days) after the last dose of the study drug.

Study medication will be administered orally QD throughout the Treatment Period of the study. Subjects randomized to receive gemcabene 600 mg will take gemcabene 600 mg QD whereas subjects randomized to receive the placebo will take placebo QD. The first dose of the study drug will be administered at the site on Day 1. On all other days during the Treatment Period, the subject will self-dose.

6.2 Efficacy Measures

The primary efficacy measure is the percent change from baseline (CFBL) to Week 12 in fasting LDL-C (hereafter referred to as “LDL-C”).

The secondary efficacy measures are:

- percent CFBL to Week 12 in LDL-C within each statin-intensity stratum (moderate, high);
- CFBL and percent CFBL to Weeks 2, 4, 8, and 12 in LDL-C;
- CFBL and percent CFBL to the average of Weeks 8 and 12 in LDL-C;
- CFBL and percent CFBL to Weeks 2, 4, 8, and 12 in non-high-density lipoprotein cholesterol (non-HDL-C), total cholesterol (TC), TG, HDL-C, and very low-density lipoprotein cholesterol (VLDL-C);
- percent of subjects achieving a LDL-C reduction from baseline of $\geq 10\%$, $\geq 15\%$, and $\geq 20\%$ at Weeks 4, 8, and 12;
- percent of subjects achieving a LDL-C value < 100 mg/dL (2.59 mmol/L) at Weeks 4, 8, and 12;
- CFBL and percent CFBL to Weeks 4, 8 and 12 in ApoB , ApoA-I, ApoA-II, ApoA-V, ApoC-II, ApoC-III, ApoE, and lipoprotein(a) (Lp[a]);
- CFBL and percent CFBL to Week 12 in hsCRP, SAA, adiponectin, and fibrinogen; and
- CFBL to Week 12 in Framingham Risk Score (ie, 10-year risk of developing cardiovascular disease [CVD]).

The exploratory efficacy measures are:

C [REDACTED]

[REDACTED]

[REDACTED]

[REDACTED]

[REDACTED]

[REDACTED]

- **CI** [REDACTED]

Developed using Framingham Heart Study data,^{1,2} the Framingham Risk Score is an estimate of a subject's 10-year risk of developing CVD which is computed using sex-specific algorithms that contain the following risk factors: age, systolic blood pressure (SBP), smoking status, TC, HDL-C, treatment for hypertension, and diabetes status. Smoking status refers to cigarette smoking status and will be collected once for each subject during the study and recorded on the Medical History CRF. Specifically, a smoker is defined as a subject where smoking is recorded on the Medical History CRF with a start date on or before first dose (ie, smoking start date \leq day of first dose) and a stop date on or after first dose (ie, smoking stop date \geq day of first dose). Partial and missing dates will be imputed using rules in [Appendix 2](#). [Appendix 3](#) contains anatomical therapeutic chemical (ATC) categories and descriptions that will be used to identify treatment for hypertension. A subject is considered to be receiving treatment for hypertension at baseline if there is at least 1 treatment for hypertension with a start date on or before first dose (ie, medication start date \leq day of first dose) and a stop date on or after first dose (ie, medication stop date \geq day of first dose). Partial and missing dates will be imputed using rules in [Appendix 2](#). CVD comprises coronary death, myocardial infarction, coronary insufficiency, angina, ischemic stroke, hemorrhagic stroke, transient ischemic attack, peripheral artery disease, and heart failure. Please refer to [Appendix 4](#) for the sex-specific algorithms that will be used to compute each subject's Framingham Risk Score at baseline and Week 12.

6.3 Safety Measures

Safety and tolerability measures include adverse events (AEs), safety laboratory parameters (chemistry, hematology, coagulation, and urinalysis), 12-lead electrocardiograms (ECGs), physical examinations, vital signs, and weight. Regarding safety laboratory parameters, particular attention will be paid to hepatic (eg, alanine aminotransferase [ALT]/aspartate aminotransferase [AST], bilirubin, alkaline phosphatase [ALP]), renal (eg, blood urea nitrogen [BUN], serum creatinine, protein/creatinine ratio, albumin/creatinine ratio, neutrophil gelatinase-associated lipocalin [NGAL], urinalysis sediments, pH, electrolytes), and skeletal muscle (ie, creatine kinase) toxicities. AEs will be coded using the Medical Dictionary for Regulatory Activities (MedDRA) version 19.1.

7 STUDY POPULATIONS

7.1 Analysis Populations

A summary table containing the number of subjects in each of the populations defined below will be provided.

7.1.1 Full Analysis Set

The Full Analysis Set (FAS) comprises all randomized subjects who receive at least 1 dose of the study drug and have at least 1 post-baseline efficacy assessment. Subjects will be classified according to the treatment they were randomized to. Efficacy analyses will be conducted using the FAS.

7.1.2 Per-Protocol Set

The Per-Protocol Set (PPS) includes all FAS subjects who complete the 12-week Treatment Period without major protocol deviations. Subjects will be classified according to the treatment they were randomized to. The PPS will be determined by the sponsor prior to treatment unblinding at the end of the study. The PPS will be used to assess the robustness of analysis results. Subjects excluded from the PPS and the reason for exclusion will be provided in the listings.

7.1.3 Safety Analysis Set

The Safety Analysis Set (SAS) consists of all randomized subjects who receive at least 1 dose of the study drug. Subjects will be classified according to the treatment they actually received. Safety analyses will be conducted using the SAS.

8 CHANGES IN CONDUCT OR PLANNED ANALYSES FROM THE PROTOCOL

Although the National Cholesterol Education Program Adult Treatment Panel III (NCEP ATP-III) Risk Category was specified in the protocol as a secondary endpoint, this was not computed because the CRFs did not collect all of the necessary information (family history of premature coronary heart disease).

Additionally, although the percent of diabetic subjects with > 5% decrease in dosage of anti-diabetes pharmacologic therapy from baseline to Week 12 was cited in the protocol as an exploratory endpoint, this analysis will not be conducted.

Although the protocol indicates that secondary analyses will be performed on subjects on and not on ezetimibe, these will not be done due to an insufficient number of subjects on ezetimibe.

Even though confirmatory analyses for secondary and exploratory analyses were detailed in the protocol, these will not be conducted.

Additionally, although percent CFBL to Weeks 2, 4, and 8 in LDL-C was not specified in the protocol, these analyses will be performed for completeness.

9 OVERALL STATISTICAL CONSIDERATIONS

9.1 Sample Size Computation

The primary efficacy endpoint is the percent CFBL to Week 12 in LDL-C, with the primary focus on the overall set of randomized subjects. The efficacy within each baseline stable statin-intensity (high and moderate) stratum is also of interest for this study; thus, the study is powered for analysis within each baseline statin-intensity stratum. A sample size of 26 randomized subjects in the gemcabene 600 mg group and 26 randomized subjects in the placebo group within each baseline statin-intensity stratum is expected to provide 80% power to detect a difference of 17% in the percent CFBL to Week 12 in LDL-C between the gemcabene treatment group and the placebo group within each baseline statin-intensity stratum. This calculation is based on a 2-sided t-test at the 5% level of significance ($\alpha = 0.05$), a common standard deviation (SD) of 20, and a drop-out rate of 10%. The sample size of 26 randomized subjects in each baseline statin-intensity stratum in the gemcabene 600 mg group gives a total of 52 randomized subjects in the gemcabene 600 mg group. Twenty-six randomized subjects in each baseline statin-intensity stratum in the placebo group gives a total of 52 randomized subjects in the placebo group. Thus, the total study sample size is 104 randomized subjects.

9.2 General Conventions

In general, variables will be summarized using summary statistics. Frequency and percentages will be used for categorical variables whereas mean, SD, median, minimum, and maximum will be used to summarize continuous variables. Decimal precision for continuous variables will be based on the mean value; the median will contain the same number of decimal places as the mean, the SD will contain one more decimal place than the mean, and the minimum and maximum will contain one less decimal place than the mean. Typically, the mean will contain one more decimal place than actual values but decimal precision may vary in order to obtain an organized and understandable table or listing.

The first day of administration of randomized study medication (first dose) is defined as Study Day 1 or Day 1. All other study days will be computed relative to Day 1. For events on or after Day 1, study day for a particular event will be calculated as:

$Date_{event} - Date_{first\ dose} + 1$. For events before Day 1, study day for a particular event will be calculated as: $Date_{event} - Date_{first\ dose}$. Day 0 will not be used.

All statistical testing will be 2-sided and performed at the $\alpha = 0.05$ level. No multiplicity adjustments will be made for testing multiple secondary and exploratory efficacy outcomes. Given the large number of secondary and exploratory efficacy outcomes, p-values associated with such outcomes will be considered descriptive. As it is possible that some significant results could occur due to chance alone, undue consideration will not be given to isolated significant differences; rather, interpretation will be made based on patterns of significant differences and consistency with the primary outcome.

For a given parameter (eg, y) CFBL will be calculated as $y_t - y_b$, where y_t is a given subject's value t weeks post-baseline and y_b is a given subject's value at baseline. CFBL will be computed

for subjects with a baseline value and a post-baseline value. In order to be included in a CFBL analysis for a given parameter, a subject must have a baseline value. If a subject does not have a baseline value, they will be excluded from the CFBL analysis. If a subject is missing a post-baseline value, last observation carried forward (LOCF) will be used to impute the post-baseline value; only post-baseline values will be used for imputation. For example, if a value at Week 8 is missing and the corresponding Week 4 value is not missing, the Week 4 value will be carried forward. Considering that only post-baseline values can be used for imputation, it follows then that Week 2 summaries will only contain observed case data as there will be no post-baseline values to carry forward. Percent CFBL for a given subject and parameter will be computed as $\left(\frac{y_t - y_b}{y_b}\right) * 100$ (ie, CFBL divided by the baseline value and multiplied by 100). Percent CFBL will only be computed for subjects with a CFBL value. Additionally, subjects with a value of 0 at baseline will not have percent CFBL computed.

For efficacy parameters, end of treatment is defined as the last non-missing post-baseline value collected while on treatment or within 2 days of treatment (last dose) for a given subject. For safety parameters, end of treatment is defined as the last non-missing post-baseline value collected while on treatment or within 5 days of treatment (last dose).

The primary efficacy analysis will be conducted using analysis of covariance (ANCOVA). Secondary and exploratory analyses will utilize a similar approach except when the outcome of interest is binary; when the outcome of interest is binary, a logistic regression will be performed.

9.3 Baseline Definitions

Baseline for a given parameter is generally defined as the last assessment prior to the first dose of the study drug but varies depending on the parameter:

- Baseline for lipids (ie, LDL-C, non-HDL-C, TC, TG, HDL-C and VLDL-C) is defined as the average of the corresponding parameter's last 2 non-missing values between (and including) Screening and pre-dose Day 1. If only 1 value is available, it will be used for baseline.
- Baseline for apolipoproteins (ie, ApoB, ApoA-I, ApoA-II, ApoA-V, ApoC-II, ApoC-III, ApoE, and Lp[a]), inflammatory biomarkers (ie, hsCRP, SAA, adiponectin and fibrinogen), serum C1, fasting insulin, and FPG is defined as the corresponding parameter's last non-missing value between (and including) Screening and pre-dose Day 1.
- Baseline for HbA1c is defined as the value from the first visit (Pre-Screening or Screening Visit).
- Baseline for ECGs, vital signs, body mass index (BMI), weight, and safety laboratory parameters (ie, chemistry, hematology, coagulation, and urinalysis parameters) is defined as the last pre-dose measurement (pre-dose Study Day 1 or before) for the corresponding parameter.
- Baseline Framingham Risk Score for each subject will be computed using the following variables at the following time points: age at the Screening Visit, baseline TC (previously defined), baseline HDL-C, baseline SBP, treatment for hypertension at Day 1, smoking status at Day 1, and diabetes status at the Screening Visit.

9.4 Handling of Missing Data

Missing values at baseline will not be imputed in any situation. For efficacy analyses, values missing post-randomization will be imputed using LOCF (unless otherwise specified); only post-randomization values on treatment will be used for imputation. For example, if a subject has Week 12 efficacy parameters measured more than 2 days after their last dose, their Week 12 efficacy values will be imputed using the last non-missing value while on treatment (eg, Week 8). The imputed values will be used in summaries and analysis. For safety analyses, observed case data will be used.

Imputation will not be conducted for AEs missing severity or relationship to study medication. AEs missing severity will be excluded from summaries of AEs by severity. Adverse events missing relationship will be excluded from summaries of related AEs.

Rules for partial and missing dates for prior and concomitant medications and smoking status are given in [Appendix 2](#).

Drug interruptions with partial start and/or stop dates will be assumed to be 1 day in length, and will be assumed to have occurred in the visit interval prior to when the interruption was collected (eg, if a drug interruption with partial dates was collected at the Week 8 visit, we will assume that the interruption occurred between the previous visit [eg, Week 4] and the Week 8 visit).

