6.6 Early Termination Visit and Withdrawal Procedures

Subjects must fast (at least 10 hours) prior to this visit.

For subjects who are withdrawn from the study prior to completion, the following procedures will be performed at the ET Visit:

- Perform full physical examination;
- Record vital signs and weight;
- Collect urine sample for urinalysis including urine protein:creatinine ratio, albumin:creatinine ratio and NGAL;
- Perform serum pregnancy test (for women of child-bearing potential only);
- Obtain blood sample for the following:
 - Safety chemistry panel, coagulation, and hematology;

- Fasting lipid panel, LDL-C ultracentrifugation (in subjects with TG \geq 400 mg/dL) and apolipoproteins;
- Fasting insulin and FPG
- CI
- HbA1c;
- hsCRP, SAA, adiponectin and fibrinogen; and
- Reserve samples;
- Perform 12-lead ECG;
- Assess and document study drug compliance; and
- Assess adverse events and update concomitant medications.

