9.3 Statistical Methods

9.3.1 Analysis of Efficacy

9.3.1.1 Primary efficacy analyses

The primary efficacy endpoint is the percent change in fasting LDL-C from baseline to Week 12. The primary efficacy endpoint will be analyzed using analysis of covariance (ANCOVA) with percent change from baseline to Week 12 in LDL-C as the dependent variable; treatment, baseline statin intensity (high-intensity; moderate-intensity), and baseline diabetes (yes or no) as factors; and baseline fasting LDL-C as a covariate. Baseline will be defined as the average of the LDL-C values at Screening/Visit S1 and pre-dose Day 1/Visit T1. The ANCOVA will be performed using the FAS, with subjects included in their randomized treatment group regardless of the treatment they actually received. Missing values for Week 12 will be imputed using last observation carried forward (LOCF); only post-baseline values will be used for the imputation. The least-squares mean (LSM) and standard error (SE) will be provided for both treatment groups, along with the placebo-corrected LSM, its 95% confidence interval (CI), and associated p-value. A 2-sided test with a significance level of 0.05 will be used for the comparison of gemcabene 600 mg to the placebo group. If non-normality is detected, then either the data will be transformed so that it is normally distributed or a nonparametric test will be used.

A confirmatory analysis of the primary efficacy endpoint will be performed using the PPS.

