9.6 Visit Windows

Visit windows will be used to classify scheduled (except the Follow-up Visit), unscheduled, and early termination (ET) visits according to [Table 2](#). below to ensure that all visits have the potential to contribute to summaries. If 2 or more visits occur within the same analysis window, data from the visit closest to the target day will be used in summaries and/or analysis; if the visits are the same distance from the target day, data from the later date will be used. Data for laboratory parameters scheduled to be measured post-randomization at only the Week 12 or ET Visit (ie, HbA1c, C1 hsCRP, SAA, fibrinogen, adiponectin, FPG, and insulin) will be summarized under the Week 12 Visit. If there is more than one value, the latest will be used. For efficacy, parameters measured after last dose + 2 days will not be considered. Except for adverse events, for safety, parameters measured after last dose + 5 days will not be considered.

Table 2. Visit Windows for Assessments Done at Day 1, Weeks 2, 4, 8, and 12^a

Visit	Target Study Day	Visit Window
Day 1	1	(1)
Week 2	15	(2, 22)
Week 4	29	(23, 43)
Week 8	57	(44, 71)
Week 12	85	> 71

^a. As Apo and select urinalysis parameters are not measured at Week 2, the Visit Window for Week 4 for Apo and urinalysis parameters is (2, 43). Remaining urinalysis parameters are not measured at Week 2 or Week 8; thus, the Visit Windows for Week 4 and Week 12 are (2, 57) and > 57, respectively.

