11 EFFICACY PARAMETERS

11.1 Primary Analysis

The primary efficacy endpoint (percent CFBL to Week 12 in LDL-C) will be analyzed using ANCOVA and the FAS population. The null hypothesis to be tested is that there is no difference in the expected percent CFBL to Week 12 in LDL-C between the active treatment (subjects treated with gemcabene 600 mg) and placebo (subjects treated with placebo) groups after adjusting for baseline statin-intensity stratum, baseline diabetes status, and baseline LDL-C. Explicitly, in the ANCOVA, percent CFBL to Week 12 in LDL-C will be the dependent variable whereas randomized treatment group (gemcabene 600 mg or placebo), baseline statin-intensity stratum (moderate or high), and baseline diabetes status (yes or no) will be included as factors, and baseline LDL-C will be included as a covariate. LOCF will be used to impute missing values for Week 12; only post-baseline values will be used for imputation. The least-squares mean (LSM) and standard error (SE) for percent CFBL to Week 12 in LDL-C for each treatment group and the least-squares mean and 95% confidence interval (CI) of the treatment difference will be produced from the model using type III sums of squares to estimate the magnitude of the treatment effect. The following SAS code will be used to conduct the ANCOVA:

```
proc glm data=data;  
  class Drug(ref="Placebo") Diabetes StatinStrat;  
  model pctCFBL = Drug Diabetes StatinStrat Base / solution;  
  lsmeans Drug / stderr pdiff out=adjmeans;  
run;
```

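### The SAP's last-dose + 2 days rule makes the primary Week 12 LDL-C analysis on-treatment, a departure from the protocol that Section 8 does not declare and no planned analysis measures

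*SAP*

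**What the plan says.** **Protocol.** Section 9.3.1.1 analyses percent change in LDL-C at Week 12 by ANCOVA in the Full Analysis Set (FAS), grouped as randomized. On missing data it says: "Missing values for Week 12 will be imputed using last observation carried forward (LOCF); only post-baseline values will be used for the imputation". It sets no limit relative to the last dose.

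**SAP, general rules.** Section 9.4 restricts LOCF to on-treatment values and goes beyond missing data: "if a subject has Week 12 efficacy parameters measured more than 2 days after their last dose, their Week 12 efficacy values will be imputed" from the last on-treatment value. Section 9.6 adds: "For efficacy, parameters measured after last dose + 2 days will not be considered". Both apply to efficacy generally, so they govern the primary endpoint. The end-of-treatment definition for efficacy in 9.2 uses the same 2-day limit.

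**SAP, primary analysis.** Section 11.1 keeps the protocol's wording: "LOCF will be used to impute missing values for Week 12; only post-baseline values will be used for imputation". The LOCF sentence in 9.2 is similar: "last observation carried forward (LOCF) will be used to impute the post-baseline value; only post-baseline values will be used for imputation". Neither mentions the cut-off.

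**SAP Section 8.** Five changes from the protocol are listed: the NCEP ATP-III category, the anti-diabetic dose endpoint, the ezetimibe subgroups, the confirmatory runs for secondary and exploratory endpoints, and some added visits ("although percent CFBL to Weeks 2, 4, and 8 in LDL-C was not specified in the protocol, these analyses will be performed for completeness"). The 2-day rule is not among them.

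**Robustness.** The only alternative run planned for the primary endpoint uses the Per-Protocol Set (PPS), which "includes all FAS subjects who complete the 12-week Treatment Period without major protocol deviations".

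**The concern.** The protocol fills gaps; the SAP also sets aside LDL-C values that were measured. A reader of 11.1, or of Section 8, would take the reported result to follow the protocol's rule when it rests on an on-treatment data selection. An on-treatment target may be defensible, but it answers a different question from one that uses values measured after drug was stopped. Protocol 1.4 says the results will help inform Phase 3, so the size of the estimate matters as well as its p-value. As planned, nobody could tell how far the two versions differ.

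**Working it through.** **1. The plan's own figure.** Inputs from protocol 9.1 and SAP 9.1: difference 17, SD 20, two-sided alpha 0.05, power 80%, drop-out 10%. The noncentral t gives 23 evaluable subjects per arm (power 80.5%). Then 23/0.90 = 25.6, rounded up to 26, and 26 x 2 arms x 2 strata = 104. The sample size reproduces and is not in dispute.

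**2. Who is affected.**
- Subjects still dosing are not: under protocol 6.4.5 the Week 12 draw is on or before Day 85 and study drug is given at that visit.
- Withdrawn subjects can be. Protocol 6.6 says "For subjects who are withdrawn from the study prior to completion, the following procedures will be performed at the ET Visit", and the list includes a fasting lipid panel. Neither 6.6 nor the ET column of Appendix A ties the visit to the last dose.
- Subjects who stop drug but attend Week 12 can be. Protocol 9.3.2 counts withdrawal from treatment separately from withdrawal from the study.

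**3. What changes for them (hypothetical cases).**
- Last dose Day 40, ET draw Day 50: the protocol's rule carries the Day 50 value to Week 12. The SAP discards it and carries Week 4. Neither is a measured Week 12 outcome; only the source differs.
- Last dose Day 70, ET draw Day 80: the draw falls in the SAP's Week 12 window (after Day 71), but the SAP discards it and carries Week 8.
- Only post-baseline LDL-C is more than 2 days after the last dose: the subject meets the FAS definition but has no primary value.

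**4. Size, as an illustration.** Assume k gemcabene subjects have a late value replaced, each has lost a share w of the 17-point effect, the carried value keeps the full effect, and placebo values do not change. Neither k nor w is in the documents.

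SE = 20 x sqrt(2/52) = 3.92. Shift toward gemcabene = 17 x w x k / 52.

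| k | w | Shift (points) | Shift / SE |
|---|---|---|---|
| 1 | 1 | 0.33 | 0.08 |
| 3 | 0.5 | 0.49 | 0.13 |
| 5 | 0.5 | 0.82 | 0.21 |
| 5 | 1 | 1.63 | 0.42 |

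**5. Effect on the overall test.** Keep the measured values with a fraction f = 0.10 of the gemcabene arm affected. The mean difference is 17(1 - fw), and the gemcabene variance is 400 + f(1 - f)(17w)^2.
- w = 1: difference 15.3, pooled SD 20.32, power 96.7% with 52 per arm.
- w = 0.5: difference 16.15, pooled SD 20.08, power 98.2%.
- No loss: 99.0%.

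A simulation of the k = 5, w = 1 case (40,000 trials, assumed between-visit correlation 0.6, two-sample t-test) gave 97.0% keeping measured values against 99.0% under the SAP rule. Type I error was 4.9% against 5.0%.

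**6. Direction.** Step 4 fixes the sign by assumption. Protocol Appendix E recommends stopping the statin under its hepatic criteria, and 4.3 allows withdrawal when a prohibited medication is needed. Either can move a late value in either arm. Protocol 1.3 puts moderate-intensity statin lowering at 30% to just under 50%. Complete loss of 30% to 50% raises LDL-C by 1/0.70 - 1 = 43% to 1/0.50 - 1 = 100%, or 43/52 = 0.82 to 100/52 = 1.92 points per subject. One such placebo subject added to k = 5 makes the net shift anywhere from 1.63 - 0.82 = +0.8 to 0.82 - 1.92 = -1.1.

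**7. Can the PPS show it?** No. It excludes non-completers, and 11.1 repeats the primary analysis on it, so the same rule applies there.

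**The case against.** - **The rule is not hidden.** A reader might infer an undisclosed change. The documents do not support that: 9.4 gives a worked example, 9.6 repeats the cut-off, and 9.2 uses the same limit for end of treatment. What is missing is its declaration as a departure.
- **The SAP does not contradict itself.** On-treatment values are a subset of post-baseline values, so 9.2 and 11.1 are general and 9.4 is specific. This stands; a cross-reference is enough.
- **Randomized grouping is kept.** Also right. On-treatment describes which values are used, not how subjects are grouped. The protocol's LOCF itself carries on-treatment values forward for dropouts with no later sample.
- **The objective speaks of twelve weeks of treatment.** That may support an on-treatment target, but the SAP does not make the argument.
- **An ET draw is not a protocol Week 12 value, and the SAP's window is already closed.** The protocol allows no Week 12 visit after Day 85, and the last-dose limit bounds the SAP's otherwise open window. So the window is no fault as the SAP stands; an upper day is needed only for a run without the cut-off.
- **The illustration is generous.** Five of 52 is about the whole planned 10% drop-out (5.2), with every such subject giving a late sample. This stands, so the figures show scale and are not a forecast.

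**Conclusion.** The point holds as an undeclared departure from the protocol that affects the data used in the primary analysis. It should be fixed, but it does not threaten the overall test. On the assumptions in steps 4 and 5, the estimate could differ by about 0.3 points for one subject with full loss and by 0.8 to 1.6 points for five of 52 with half to full loss, with overall power about 97% against 99%. A reader might infer that the rule favours gemcabene or could create a positive result. The documents support neither: they give no count of affected subjects, no size for the effect lost off drug, and no fixed direction.

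**What to change.** 1. Declare the on-treatment rule and its reason in SAP Section 8, and cross-refer to it in 11.1.
2. State before unblinding which version is primary. The protocol's rule is the default unless the change is justified.
3. Run the same FAS ANCOVA under the protocol's rule. Keep every measured LDL-C in the Week 12 window, and use LOCF from any post-baseline value only when Week 12 is truly missing. The sponsor should choose an upper day for that window before unblinding.
4. Report by arm how many measured values the rule replaced and how many FAS subjects have no primary value.

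The cost is some SAP wording and one more run on data already collected. The downside is two estimates to explain, one of them possibly slightly less favourable. Precision barely changes: the simulated SE was 3.94 keeping measured values against 3.93 under the SAP rule, with five of 52 and full loss. The extra run does not recover outcomes for subjects who gave no sample after stopping drug.
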